Effects of Blood Flow Restriction Training Combined with Abdominal draw-in Maneuver on Transverse Abdominis Strengthening

CRREC-109-007

Date: 2021/09/14

I. Study Protocol:

Healthy adults (age ranged 18-34 years and BMI between 18.5~24.99) were randomly recruited in the study. For the intervention group, an inflatable cuff (14 cm in width * 84 cm in length) is warped around abdominal muscles below ribs which may cause to at least 60% restriction of blood flow detected by Power Doppler ultrasonography. All participants are instructed to perform ADIM both condition of BFR and BFR-free twice a week, for four weeks. Core muscle thickness will be measured at rest and at draw-in by 2D ultrasound. Abdominal core stability, strength and endurance test by double leg lowering test, dynamometer and abdominal static endurance test.

II. Statistical Analysis Plan

Two-way mixed design ANOVA test is used to measure the group difference, time difference and interaction. Using Bonferroni post hoc test to analyze the difference among timepoints within group and Independent t test for the difference between two groups.

III. Results

1. Muscle thickness measured by ultrasound

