1.1 Transverse abdominis

Measured by two-way mixed design ANOVA, there is no main time effect, group effect and interaction of time and group of mean bilateral thickness of transverse abdominis (TrA) at rest. At draw-in, there is no main time effect but group effect and interaction of time and group of mean bilateral thickness of TrA. Of muscle thickness change between draw-in and resting, there are main time effect, group effect and interaction of time and group of mean bilateral thickness of TrA.

Before training, there is no significant difference between ADIM+BFR group and ADIM group of TrA thickness at rest, draw-in and thickness change(p>0.05). After 3 weeks of training, there is no significant difference between ADIM+BFR group and ADIM group of TrA thickness at rest. ADIM+BFR group shows significant thicker muscle at draw-in and thickness change. After 4 weeks of training, there is no significant difference between ADIM+BFR group and ADIM group of TrA thickness at rest. ADIM+BFR group shows significant thicker muscle at draw-in and thickness change. One week after the end of training, there is no significant difference between ADIM+BFR group and ADIM group of TrA thickness at rest. ADIM+BFR group shows significant thicker muscle at draw-in and thickness change.

ADIM+BFR group shows no significant difference of TrA thickness among timepoints at rest. There is significant increase at week 4 and one week after the

end of training compared with baseline and at week 4 compared with week 3 at draw-in. There is significant thickness change at week 3, 4 and one week after the end of training compared with baseline. There is no significant difference at rest, at draw-in and thickness change among timepoints in ADIM group.

2. Abdominal functional test

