2.1 Abdominal core stability

Measured by two-way mixed design ANOVA, there are main time effect, group effect and interaction of time and group.

Before training, there is no significant difference between ADIM+BFR group and ADIM group of double leg lowering test, so as after 3 weeks of training. However, ADIM+BFR group shows significant decrease in angle of double leg lowering test after 4 weeks of training and one week after the end of training, which shows better core stability.

ADIM+BFR group shows significant different among timepoints. Compared with baseline, it shows significant decrease after 3,4 weeks of training and one week after the end of training. Furthermore, after 4 weeks of training and one week after the end of training, it shows significant different compared with week 3 and week 4.

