2.2 Abdominal strength test

Measured by two-way mixed design ANOVA, there is main time effect but no group effect and interaction of time and group.

Before training, there is no significant difference between ADIM+BFR group and ADIM group of abdominal strength test measured by dynamometer, so as after 3 weeks of training. However, ADIM+BFR group shows significant increase after 4 weeks of training and one week after the end of training, which shows better core strength.

ADIM+BFR group shows significant different among timepoints. Compared with baseline, it shows significant increase after 4 weeks of training and one week after the end of training. Furthermore, after 4 weeks of training and one week after the end training, it shows significant different compared with week 3. ADIM group shows significant different after 4 weeks of training compared with baseline.

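### Does the sentence that has every participant train with and without blood flow restriction undermine the two-group analysis?

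*Combined protocol and SAP*

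**What the plan says.** Section I (Study Protocol) has three relevant statements. Healthy adults "were randomly recruited in the study". The cuff is introduced with the words "For the intervention group, an inflatable cuff". The next sentence gives the training schedule: "All participants are instructed to perform ADIM both condition of BFR and BFR-free twice a week, for four weeks".

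Section II (Statistical Analysis Plan) sets the main model: "Two-way mixed design ANOVA test is used to measure the group difference, time difference and interaction". Bonferroni post hoc tests follow for timepoints within a group, and for the other contrast an "Independent t test for the difference between two groups".

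Section III (Results) reports two named groups, ADIM+BFR and ADIM, for every outcome. They are assessed before training, after 3 weeks, after 4 weeks and one week after training ended.

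**The concern.** The subject of the schedule sentence is all participants and its object is both conditions. Taken at face value, it describes exposure within each person and contradicts the cuff sentence just before it. It is also the only sentence that gives the training schedule, so section I alone does not settle the design.

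Two things would be at stake if the literal reading were true:

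- If participants trained under the two conditions in turn, each person would contribute to both. An independent t test and a between-subject group factor would then be the wrong analysis.
- If they trained under both conditions concurrently, there would be no BFR-free comparison at all.

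A second worry concerns how the groups were formed. The only use of the word random concerns recruitment, which is about sampling. The title speaks of effects of BFR training, and section III describes the ADIM+BFR group as showing better stability, strength and endurance. That language depends on how people came to be in each group.

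**Working it through.** The documents give no sample size, standard deviation, within-person correlation or allocation ratio, so there is no design figure to reproduce. The check sets the text against three readings.

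**Step 1. The readings side by side.**

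| Place | Separate groups | Both conditions in turn | Both conditions concurrently |
|---|---|---|---|
| Section I, cuff sentence ("For the intervention group, an inflatable cuff") | Fits | Conflicts: everyone would receive the cuff | Conflicts, same reason |
| Section II, mixed-design ANOVA | Fits: group between people, time within | Conflicts: condition and time would both be within people | Conflicts: no group factor exists |
| Section II, independent t test | Fits | Wrong test | Nothing to compare |
| Section III, baseline contrast of groups | Fits | Would need a baseline for each period; only one is reported | Nothing to compare |
| Section III, one series of four assessments around four weeks of training | Fits | Would need periods, an order and probably a washout; none is described | Does not discriminate |

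The results wording agrees with the first column. Section 2.1 has "Before training, there is no significant difference between ADIM+BFR group and ADIM group of double leg lowering test". Section 1.1 follows the comparison group over time by itself: "There is no significant difference at rest, at draw-in and thickness change among timepoints in ADIM group". Section 2.2 does the same: "ADIM group shows significant different after 4 weeks of training compared with baseline". These statements presuppose a group that trained without the cuff.

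Only the schedule sentence points away from separate groups. It is ungrammatical, and a small repair (participants in both conditions do ADIM twice a week) removes the conflict.

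**Step 2. What would change.** The outcomes are transverse abdominis (TrA) thickness at rest, at draw-in and as thickness change, then stability, strength and endurance.

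- Between-group comparisons: 6 outcomes × 4 timepoints = 24.
- Reported significant, in that order: 0 + 3 + 3 + 2 + 2 + 2 = 12.
- Baseline comparisons: 6, all reported as not significant.

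The last six of the 12 are partly a matter of reading. The sentences on the functional tests name no comparator in the clause itself, but they follow directly on between-group statements. With separate groups, 0 of the 24 comparisons need a different test.

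**Step 3. Allocation.** Neither the mixed ANOVA nor the t test has a term for how groups were formed, so the calculations are the same whatever the answer. What depends on it is the causal reading. The six non-significant baseline tests do not establish random allocation. Nor does the group-by-time interaction, which is reported for only four of the six outcomes: TrA at draw-in, TrA thickness change, stability and endurance. It is absent for TrA at rest and for strength.

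**The case for a change.** The strongest case for acting is that a protocol should define exposure itself. A reader should not have to infer it from the SAP and the results. The faulty sentence is the only one that sets the training schedule, and a likely intended meaning does not repair the text. The missing allocation method matters more. The title makes a causal claim, and no sequence method, concealment or ratio is given.

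Part of this stands. The sentence is wrong as written, and the text available here describes no allocation method. The title pages were not in that text, so a design label there cannot be excluded. Stating both facts plainly would make the document clearer.

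It does not carry further. The intended design can be recovered with confidence from the cuff sentence, the SAP and every results section. A within-participant re-analysis would be needed only if people had trained under both conditions, and nothing beyond the one sentence suggests that. Recasting the differences as associations would be needed only if allocation was not random, which silence does not show.

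One could also try to size the harm of an independent t test on paired data. Any such figure would need an assumed within-person correlation and would ignore order and carry-over effects. It would describe a design that the document does not otherwise support, so it says nothing useful about this trial.

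**Conclusion.** The concern does not call for a change to the plan. The schedule sentence is a clerical slip. The SAP already suits the parallel-group design that the rest of the document describes, and 0 of the 24 between-group comparisons, including the 12 read as significant, would be analysed differently. The unstated allocation method is a gap in description, filled by recording what was done. It changes no model, test or reported result.

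This rests on one assumption: that each participant trained only under the condition of his or her own group. The cuff sentence, the mixed-design model, the independent t test and the two groups reported for all six outcomes support it. Trial records showing that individuals trained under both conditions would overturn it. The conclusion does not assume that allocation was random. It says only that the text does not settle the matter and that the planned calculations do not depend on it.

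### Does the mixed ANOVA over four visits need a sphericity correction written into the plan?

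*Combined protocol and SAP*

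**What the plan says.** Section II of the combined protocol and SAP is two sentences long. The first names the model: "Two-way mixed design ANOVA test is used to measure the group difference, time difference and interaction". The second adds Bonferroni comparisons between timepoints within a group and independent t tests between groups. It does not list the visits and does not mention a sphericity test, an epsilon correction, a multivariate test or a covariance model.

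The visits appear only in section III: before training, after 3 weeks, after 4 weeks, and one week after training ended. The omnibus results there are:

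- TrA thickness at rest (1.1): "there is no main time effect, group effect and interaction of time and group of mean bilateral thickness of transverse abdominis (TrA) at rest".
- TrA at draw-in (1.1): "At draw-in, there is no main time effect but group effect and interaction of time and group of mean bilateral thickness of TrA".
- TrA thickness change (1.1): "there are main time effect, group effect and interaction of time and group of mean bilateral thickness of TrA".
- Core stability (2.1): "Measured by two-way mixed design ANOVA, there are main time effect, group effect and interaction of time and group"; endurance (2.3) is reported in the same terms.
- Strength (2.2): "there is main time effect but no group effect and interaction of time and group".

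No sample size, SD, correlation, F, degrees of freedom, epsilon or exact p is given.

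**The concern.** With four repeated measurements, the time and interaction F tests refer to 3 and 3(N − 2) degrees of freedom. That reference distribution is exact only if all differences between visits have the same variance. Here the gaps are three weeks, then one, then one. Later visits may well correlate more with each other than with baseline, and that breaks sphericity. An uncorrected test then rejects too often.

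The interaction is the plan's only omnibus test of whether the groups change differently over time, and four outcomes report it as present. If some of those were borderline and uncorrected, they could be overstated. Without F or p values, a reader cannot tell.

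**Working it through.** **Inputs.** From the documents: 2 groups, 4 visits (section III), and a 5% level, inferred from the single threshold shown in 1.1. Not in the documents, so assumed: 10 to 50 per group with equal allocation, complete normal data, and the within-subject covariance. The plan states no error rate or power, so there is no figure of its own to reproduce.

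**1. Which statements are exposed.** Six outcomes with two within-subject tests each give 6 × 2 = 12.

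- Reported present, 8: interaction for draw-in, thickness change, stability and endurance; time for thickness change, stability, strength and endurance.
- Reported absent, 4: both tests for TrA at rest, time for draw-in, interaction for strength.

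A Greenhouse-Geisser correction only raises the critical value, so it cannot alter the four absences. At most eight statements are open. They are not eight separate pieces of evidence, because thickness change is derived from the draw-in and rest measurements.

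**2. How large the inflation could be.** For a covariance matrix S over k = 4 visits,

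ε = k²(mean diagonal − grand mean)² / {(k − 1)[Σs² − 2kΣ(row mean)² + k²(grand mean)²]}.

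Example: unit variances, correlation 0.5 between baseline and later visits, and 0.9 among later visits. The row means are 0.625 and 0.825 (three times), and the grand mean is 0.775.

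- Numerator: 16 × 0.225² = 0.81.
- Σs² = 4 + 6 × 0.25 + 6 × 0.81 = 10.36.
- Σ(row mean)² = 0.3906 + 3 × 0.6806 = 2.4325.
- Denominator: 3 × (10.36 − 8 × 2.4325 + 16 × 0.6006) = 3 × 0.51 = 1.53.
- ε = 0.81/1.53 = 0.53.

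Simulated type I error at a nominal 5%. Rows marked * are the interaction test at 20 per group (100,000 trials per setting). The others cover both tests at 10 to 30 per group (60,000 trials).

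| Assumed covariance | ε | Uncorrected % | Greenhouse-Geisser % |
|---|---|---|---|
| Compound symmetry 0.8* | 1.00 | 5.05 | 4.61 |
| Baseline 0.7, later 0.8* | 0.93 | 5.38 | 4.58 |
| Baseline 0.5, later 0.8* | 0.73 | 6.48 | 4.74 |
| Serial correlation 0.9 per week* | 0.65 | 7.27 | 4.91 |
| Baseline 0.5, later 0.9* | 0.53 | 8.43 | 5.08 |
| Strong random slopes | 0.47 | 8.9–9.2 | 4.9–5.1 |
| Theoretical limit | 0.33 | 10.8–11.2 | 4.9–5.1 |

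Sample size between 10 and 30 per group made almost no difference. Serial correlation of 0.95 with 50% measurement noise gives 5.11% uncorrected at 20 per group, so the inflation may also be close to nil.

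**3. A bound that needs no covariance.** ε cannot be below 1/(k − 1) = 1/3. At that limit the degrees of freedom become 1 and N − 2. With 20 per group, N − 2 = 38, and the 5% critical value of F(1, 38) is 4.10. Referred to the uncorrected F(3, 114), F = 4.10 has p = 0.0084. Any effect with uncorrected p below that stays significant whatever the covariance. The same bound is 0.0076 at 10 per group, 0.0087 at 30 and 0.0089 at 50. At 20 per group, the p values at risk narrow to 0.020–0.05 if ε is 0.53, and to 0.033–0.05 if ε is 0.73.

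**4. What does not depend on sphericity.** The group main effect uses each participant's mean over visits, and the t test at each visit uses one measurement per person. The four outcomes with a reported interaction also have a reported group main effect and significant group differences at two or three visits after baseline. Examples are "ADIM+BFR group shows significant thicker muscle at draw-in and thickness change" in 1.1 and "ADIM+BFR group shows significant decrease in angle of double leg lowering test after 4 weeks of training" in 2.1. For strength, no interaction is claimed, and the group comparison rests on the visit-wise tests. The within-group Bonferroni comparisons would be affected only if they used an error term pooled over visits, which the documents do not say.

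**The case for a change.** The strongest case for a change is that the omission is real and cheap to repair. Both SAP sentences are complete, so nothing has been lost from the text, and no later section supplies a correction. The uneven spacing makes some departure from sphericity plausible, and the calculations confirm that an uncorrected test would then be liberal. One sentence naming Greenhouse-Geisser would bring the error to 4.6–5.1% in the settings tabulated. It could not turn a reported null into a positive. When sphericity holds it costs little: simulated interaction power falls from 67.3% to 65.7% with 20 per group, compound symmetry 0.8, and an assumed group difference of 0.25 SD at week 3 and 0.5 SD at the last two visits.

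The arithmetic stands. So does the remark that a reader would be helped by seeing F, degrees of freedom, epsilon and p, and by knowing whether a correction was used. That is a matter of reporting the results.

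The step to an error in the plan does not stand. It needs three things together: no correction was applied, sphericity failed materially, and an uncorrected p fell between about 0.008 and 0.05. The documents are silent on all three. The choice of correction is also partly preference. Under the same assumed shift, Greenhouse-Geisser has less power than the multivariate test in one covariance (32.4% against 47.5%, baseline 0.5 and later 0.9) and more in another (44.3% against 37.4%, serial correlation 0.9). With results already beside the plan, a new sentence could not be prospective.

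**Conclusion.** No change to the plan is called for. This is missing detail that an analyst fills within the named method, since a sphericity correction is a routine part of running a mixed ANOVA and the plan does not exclude one.

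If the tests were uncorrected and sphericity failed, the time and interaction tests would run at about 5–9% under plausible assumed covariances, with about 11% as the limit at ε = 1/3. Eight correlated omnibus statements are open at most, and none is shown to change. Group main effects and visit-wise t tests, which carry the between-group conclusions, are untouched.

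These sizes rest on assumed covariances, 10 to 50 per group, equal allocation, complete data and an inferred 5% level. The covariance-free bound needs only the group size, and varies little with it (0.0076 to 0.0089).

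### The planned mixed-design ANOVA cannot use a participant with a missed assessment unless values are imputed, and under usual defaults the per-visit t tests may rest on different people; one likelihood-based repeated-measures model would avoid both

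*Combined protocol and SAP*

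**What the plan says.** Section II, Statistical Analysis Plan, is two sentences long. The first names the main analysis: "Two-way mixed design ANOVA test is used to measure the group difference, time difference and interaction". The second names the follow-up tests: "Using Bonferroni post hoc test to analyze the difference among timepoints within group and Independent t test for the difference between two groups".

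The number of assessments has to be read from section III, Results. In 1.1, Transverse abdominis, the groups are compared before training and then three more times, for example "After 3 weeks of training, there is no significant difference between ADIM+BFR group and ADIM group of TrA thickness at rest" and, at the last assessment, "One week after the end of training, there is no significant difference between ADIM+BFR group and ADIM group of TrA thickness at rest". Week 4 lies between these. The functional tests in 2.1 to 2.3 use the same four timepoints.

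The document does not give an analysis set, a rule for missed visits, imputation, software, a sample size, degrees of freedom, or the number analysed at any visit.

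**The concern.** A classical mixed-design ANOVA works on one complete row per participant. Someone measured at three of the four assessments contributes nothing to the group, time or interaction tests unless the missing value is imputed, and no imputation is planned. An independent t test at one visit needs only that visit's value. Under usual defaults the omnibus tests are therefore complete-case and the t tests available-case.

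Three things are at stake if visits are missed:

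- **Precision.** The ANOVA discards measurements that were taken.
- **Bias.** If attendance is related to response, the completers in one arm are a selected group.
- **Coherence.** Omnibus and per-visit results could differ partly because they describe different people, and a reader could not tell, since no numbers analysed are given.

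Adding a sentence that everyone is analysed would not solve this. The named ANOVA cannot take an incomplete row, so either the method changes or imputation is added.

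**Working it through.** The plan states no power, sample size or dropout figure, so there is nothing of its own to reproduce. From the document: four assessments, hence three after baseline; two groups; a mixed-design ANOVA; t tests. Everything else below is an assumption.

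**1. Independent misses.** Let each post-baseline visit be missed with probability m, independently, with baseline always present.

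- Share kept by the ANOVA = (1 − m)³.
- Share kept by a t test at one post-baseline visit = 1 − m.
- Standard-error ratio against full data = 1/√(share kept).

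| m | ANOVA keeps | Lost | ANOVA SE ratio | t test keeps | t test SE ratio |
|---|---|---|---|---|---|
| 3% | 0.97³ = 0.913 | 8.7% | 1.047 | 97% | 1.015 |
| 5% | 0.95³ = 0.857 | 14.3% | 1.080 | 95% | 1.026 |
| 10% | 0.90³ = 0.729 | 27.1% | 1.171 | 90% | 1.054 |

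**2. Monotone dropout.** If those who leave never return, the ANOVA loses only the total dropout. With 10% in total, 1/√0.90 = 1.054, so about 5% and not 17%. The t test at the last visit then uses the same people as the ANOVA.

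**3. Bias: dropout after week 3 driven by a poor week-3 change, in one arm.** Assume SD 1 at each visit, correlation 0.7 between any two visits, and no true effect.

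- Variance of the week-3 change = 2(1 − 0.7) = 0.6, so its SD is 0.775.
- Covariance of week-4 change with week-3 change = 1 − 0.7 = 0.3. The slope is 0.3/0.6 = 0.5, so the week-4 change contrast is biased by half the shift in week-3 change among completers.
- Covariance of the week-4 value with week-3 change = 0.7 − 0.7 = 0. The raw week-4 difference, which a t test on values estimates, is not biased here.
- If exactly the lowest 10% leave, the shift is 0.1755/0.90 × 0.775 = 0.151 and the bias is 0.076 SD. For the lowest 20% it is 0.2800/0.80 × 0.775 = 0.271, giving 0.136 SD. (0.1755 and 0.2800 are the normal density at the 10% and 20% points.)
- If dropout depends on the change through a logistic curve (log-odds slope 1 to 4 per SD of a single-visit value; simulation, one million participants), the bias is 0.03 to 0.07 SD at 10% and 0.06 to 0.12 SD at 20%.

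**4. Bias: dropout after week 3 driven by a low week-3 value.** Same correlation; true difference 0.40 SD at week 3 and 0.80 SD at week 4; logistic slope 1.5 in one arm, random dropout at the same rate in the other; one million per arm.

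| Dropout | Baseline, completers (true 0) | Week 3, all measured (true 0.40) | Week 3, completers | Week 4, either analysis (true 0.80) |
|---|---|---|---|---|
| 5% | 0.047 | 0.400 | 0.464 | 0.847 |
| 10% | 0.086 | 0.401 | 0.522 | 0.886 |
| 20% | 0.157 | 0.399 | 0.625 | 0.958 |

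The two analyses disagree at week 3 because their samples differ. At week 4 they contain the same people and both are biased. Subtracting baseline, the week-4 change among completers is about right (0.886 − 0.086 = 0.800 at 10%), but the week-3 change is not (0.522 − 0.086 = 0.436 against 0.40).

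Comparing steps 3 and 4, which contrast is biased, and by how much, depends on why people leave.

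**5. No missed visits.** Every share kept is 1, both analyses use the same people, and nothing is lost or biased.

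**The case against.** The strongest reply is that this is conditional. Training runs "twice a week, for four weeks" in healthy adults aged 18 to 34, with one further assessment a week later, and attendance may have been complete. No missed visit or withdrawal is reported. That stands: neither the occurrence nor the size of any loss can be shown.

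A reader might infer that the plan itself prescribes complete-case ANOVA and available-case t tests. It does not. Exclusion from a classical ANOVA follows from the method when nothing is imputed. Available-case t tests are only a usual default; they could have been run on the same completers, or both analyses on one imputed set.

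A reader might also infer that only the ANOVA is exposed. Step 4 shows that the t tests can be biased too, and in both dropout-after-week-3 scenarios the week-4 t test and the ANOVA contain the same people.

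Section 2.2, Abdominal strength test, reports neither a group effect nor an interaction, yet favours ADIM+BFR at the last two assessments. It is tempting to blame differing samples. The document does not support that: omnibus and single-visit tests can disagree on identical complete data.

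Finally, a likelihood-based model is no cure-all. Its protection requires data missing at random, which both scenarios build in. Absence because of cuff discomfort, for example, need not satisfy it.

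**Conclusion.** The concern holds as a conditional weakness of the chosen method, worth correcting but not shown to have changed any result. Without imputation, a participant missing any of the four assessments drops out of the ANOVA, and the plan has nothing to keep the t tests on the same people.

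The size in this trial is unknown. Under the assumptions above, the standard-error cost runs from nothing (complete attendance), through about 5% (10% monotone dropout), to 17% (10% missed independently at each post-baseline visit). With 10–20% dropout in one arm driven by week-3 change, the bias in the complete-case week-4 change contrast is roughly 0.03 to 0.14 SD. That range depends on equal visit correlations of 0.7 and on how sharply dropout follows the change, so it illustrates and does not estimate.

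The plan does not rank its tests, so the interaction should not be called the trial's designated key test on the strength of this document.

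**What to change.** - **Model.** Analyse each outcome with one linear mixed model for repeated measures: group, time and group-by-time, unstructured covariance, REML, Kenward-Roger degrees of freedom. Include every participant with any measurement, in the allocated group.
- **Baseline.** Keep baseline as a response with a common mean across groups. This suits random allocation; the document says only that participants were randomly recruited, so allocation should be described. Baseline as a covariate is an alternative for the between-group contrasts, but that model cannot by itself supply the planned within-group comparisons with baseline.
- **Contrasts.** Take the between-group difference at each visit and the Bonferroni-adjusted within-group comparisons from this model, in place of separate t tests.
- **Reporting.** Give numbers analysed per group and visit. State that validity assumes missing at random and, if visits were missed, add a sensitivity analysis to that assumption.
- **Status.** Results are already reported, so label the re-analysis post hoc and show it beside the planned ANOVA.

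The cost is SAP wording and a re-run in standard software, a less familiar output than an ANOVA table, and a post hoc change of method. No new data are needed. If nobody missed a visit, one sentence saying so closes the missing-data point, and the remaining benefit is baseline adjustment.

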2.3 Abdominal endurance test

Measured by two-way mixed design ANOVA, there are main time effect, group effect and interaction of time and group.

Before training, there is no significant difference between ADIM+BFR group

and ADIM group of abdominal endurance test, so as after 3 weeks of training. However, ADIM+BFR group shows significant increase after 4 weeks of training and one week after the end of training, which shows better core endurance.

ADIM+BFR group shows significant different among timepoints. Compared with baseline and 3 weeks of training, it shows significant increase after 4 weeks of training and one week after the end of training. Furthermore, one week after the end of training, it shows significant different compared with week 3. ADIM group shows significant different after 3,4 weeks of training and one week after the end of training compared with baseline.

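### The between-group t tests have no stated multiplicity correction and no stated link to the mixed ANOVA, and strength is called better with BFR although its ANOVA shows no group effect and no interaction

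*Combined protocol and SAP*

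**What the plan says.** Section II (Statistical Analysis Plan) has two sentences. The first sets the model: "Two-way mixed design ANOVA test is used to measure the group difference, time difference and interaction". The second sets the follow-up tests: "Using Bonferroni post hoc test to analyze the difference among timepoints within group and Independent t test for the difference between two groups". The section names no primary outcome or visit, states no significance level, and does not say whether the t tests depend on an ANOVA result.

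Section III, 2.2 (Abdominal strength test) reports for the ANOVA that "there is main time effect but no group effect and interaction of time and group". It then reports no group difference before training or at week 3, and continues: "ADIM+BFR group shows significant increase after 4 weeks of training and one week after the end of training, which shows better core strength". The next paragraph gives changes over time within each group. For ADIM+BFR: "Compared with baseline, it shows significant increase after 4 weeks of training and one week after the end of training". For the comparator: "ADIM group shows significant different after 4 weeks of training compared with baseline".

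**The concern.** The effect of adding BFR is a between-group contrast. The SAP states a correction for the comparisons that do not estimate that contrast (visits within one arm) and none for those that do. It also does not say which result decides when a visit-level t test and the ANOVA disagree.

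For strength, the conclusion and the ANOVA do disagree, and the conclusion went against the ANOVA with no rule permitting it. A reader would take from section 2.2 that BFR improved strength beyond ADIM alone, which the group effect and interaction do not show. For the other outcomes, a reader cannot tell which visit-level differences would remain after correction.

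**Working it through.** The plan gives no error rate, sample size or power, so there is no figure of its own to reproduce.

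**1. Was the ANOVA used as a gate in practice?** No. Section 1.1 reports no time, group or interaction effect for transverse abdominis (TrA) thickness at rest, yet gives a group comparison at every visit.

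**2. What does the strength sentence compare?** Sections 2.1 to 2.3 share one layout: ANOVA, then a between-group paragraph, then a within-group paragraph. The strength sentence continues the between-group paragraph. Stability supports this reading: its between-group paragraph reports no difference at week 3, while its within-group paragraph includes week 3 ("Compared with baseline, it shows significant decrease after 3,4 weeks of training and one week after the end of training"). Endurance uses the same form as strength ("ADIM+BFR group shows significant increase after 4 weeks of training and one week after the end of training, which shows better core endurance"). For strength and endurance, however, the visits named are the same in both paragraphs, so the text does not settle it.

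- If between-group: two t tests with no stated correction are set against an ANOVA with no group effect and no interaction.
- If within-group: a gain in one arm cannot show superiority, and the other arm also changed by week 4.

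On both readings the ANOVA does not support the claim. I read the strength ANOVA wording as neither a group effect nor an interaction, in line with the parallel wording for TrA at rest.

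**3. Error rate of the rule, one outcome.**

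- Inputs: three post-baseline visits (week 3, week 4, one week after training), from section III; 0.05 two-sided per test, assumed from the only threshold shown (in section 1.1).
- If the tests were independent: 1 - 0.95^3 = 0.143.
- Repeated measures are correlated, so the null case was simulated with compound symmetry, 10 to 30 per group and visit correlation 0.5 to 0.9 (all assumed). At least one false positive occurs in 0.082 to 0.129 of trials, about 8-13%. At correlation 0.3 it reaches 0.138.
- At least one significant post-baseline t test together with a non-significant group effect and interaction: about 3-8% of null trials per outcome (correlation 0.3 to 0.9).

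**4. Error rate after correction, one outcome.**

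- Bonferroni over three visits: 0.05/3 = 0.0167 per test. If independent, 1 - (1 - 0.0167)^3 = 0.049; simulated, 0.029 to 0.050.
- Interaction gate alone, t tests left at 0.05: 0.006 to 0.028 when the outcome has no effect at any visit.
- The gate alone does not protect an outcome with a real effect at some visits. Such an outcome tends to pass, and its remaining visits are then tested at 0.05 each. Hence the adjustment inside the gate.

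**5. Price of the visit-level adjustment.** The smallest significant difference, in SD units, is t(crit) × √(2/n), with n per group. Power is for an assumed true difference of 1.0 SD, from the noncentral t distribution with noncentrality 1/√(2/n).

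| n per group (assumed) | Level | t(crit) | Smallest significant difference | Power at 1.0 SD |
|---|---|---|---|---|
| 20 | 0.05 | 2.024 | 2.024 × 0.316 = 0.64 SD | 87% |
| 20 | 0.0167 | 2.505 | 2.505 × 0.316 = 0.79 SD | 74% |
| 10 | 0.05 | 2.101 | 2.101 × 0.447 = 0.94 SD | 56% |
| 10 | 0.0167 | 2.639 | 2.639 × 0.447 = 1.18 SD | 37% |

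These are for Bonferroni before the gate is applied. Holm is never less powerful than Bonferroni; the gate can lower power further.

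**The case against.** **The t test is also prespecified.** Section II lists both analyses and ranks neither, so giving the interaction priority is a choice the plan does not dictate. That stands. The criticism is that no rule was written. The gate proposed below is one reasonable rule among several.

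**The 8-13% is not the rate for the strength claim as reported.** This stands too. The claim covers week 4 and the follow-up visit together. Both significant in favour of BFR occurs in only about 0.4-1.6% of null trials under the same kind of assumptions. With a non-significant group effect and interaction as well, it is about 0.1% at most. The full reported pattern is also rare under an assumed true 0.8 SD effect at those two visits (0-1.4%). These rates therefore say little about whether the strength finding is true. Visit-level t tests can be significant while an interaction is not, so the results are not impossible.

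**If the strength sentence is within-group, it is not a multiplicity problem.** Correct: the planned Bonferroni would already cover it, and the error would be one of interpretation. The claim would still lack support.

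**Stronger readings a reader might infer.** One is that strength has no BFR effect; a non-significant interaction does not show that. Another is that the positive findings as a whole are probably false, since 18 independent tests (6 outcomes × 3 visits) give 1 - 0.95^18 = 0.603. That figure assumes independence and no effect on any outcome. The report gives both a group effect and an interaction for four of the six: draw-in thickness, thickness change, stability and endurance. A third is that no correction was applied. The documents show only that none is stated; they give no adjusted levels or exact p-values.

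**Conclusion.** The concern holds in two linked parts. The SAP leaves the between-group t tests without a stated correction and without a stated relation to the ANOVA. For strength, the report claims superiority that its ANOVA does not support on either reading of the sentence.

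The 8-13% per outcome measures how loose the rule is, under assumed sample size, correlations and a 0.05 level. It is not evidence against any particular result. Draw-in thickness, thickness change, stability and endurance keep their reported group effect and interaction; only statements about individual visits are affected. Which of those would remain significant cannot be determined from the documents. The point should be fixed, chiefly for strength.

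**What to change.** 1. In section 2.2, withdraw the claim of superior strength for ADIM+BFR, or label it exploratory and not supported by the ANOVA. State whether the increase is between-group or within-group.
2. In section II, state that visit-level between-group t tests are interpreted only for outcomes with a significant group-by-time interaction. Within each such outcome, adjust the three post-baseline t tests by Holm or Bonferroni (0.0167 per test for Bonferroni). Strength then has no interpretable visit-level test, since its interaction is reported as absent.
3. Disclose that this rule was added after the results were known.

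The cost is rewording and recalculation from existing data. The downside is lost visit-level significance: at an assumed 20 per group, the smallest significant difference rises from 0.64 to 0.79 SD under Bonferroni. The rule limits error within each outcome, not across all six; claims across outcomes would need a further choice, such as a named primary outcome, which the plan does not make.
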